Title: The Effect of Oral Guaifenesin on Pediatric Chronic Rhinitis: A Pilot Study

NCT #: NCT01364467

Document approval date: February 25, 2019

Document Type: Protocol

The Effect of Oral Guaifenesin on Pediatric Chronic Rhinitis: A Pilot Study

Principal investigator:

[name]

Department of Otolaryngology – Head and Neck Surgery

Virginia Commonwealth University

Richmond, VA 23219

Co-investigator:

[name] [name], MBA, FRCPC

Department of Pediatrics

Virginia Commonwealth University

Richmond, VA. 23219

Introduction

Rhinosinusitis accounts for over 2 billion dollars in over the counter medication sales¹ and is one of the most common infections in the United States. In children, rhinosinusitis is estimated to account for 4.2% of all visits to pediatricians' offices during the winter months, and 17.3% of visits related to cough or cold symptoms². Many factors such as atopy, anatomic obstruction and immunodeficiency predispose patients to developing rhinitis. Chronic rhinosinusitis (CRS), defined as a constellation of symptoms involving nasal congestion and obstruction, drainage, and thickened tenacious nasal secretions lasting for a period longer than 3 months³, is an especially troubling entity in children.

Therapies for chronic rhinitis are aimed at alleviating these symptoms and frequently include the use of antihistamines, decongestants, and topical nasal sprays. Guaifenesin, a mucus expectorant derived from guaiac resin of the wood *Guajacum officinale* Linne⁴, has been used for many years in the treatment of both acute and chronic rhinitis in an over-the-counter preparation. Other indications for its use include the treatment of cough and in cold formulations for adults and children. The mechanism of guaifenesin's action has been theorized to result from enhancement in mucus secretion from lower airway submucosal glands, with subsequent increase in total mucus volume and diminished mucus viscosity⁴. A number of reports have shown subjective improvements in nasal symptom scores using guaifenesin^{5,6,7,8}; however, to date no randomized, controlled studies have been conducted to show clear, objectively determined benefit in pediatric patients⁷. We propose to investigate the effectiveness of guaifenesin in the relief of nasal symptoms in children with CRS using the sinonasal 5 survey (SN-5). We will also measure nasal airway volume using acoustic rhinometry, and nasal secretion mucociliary clearability and dynamic viscoelasticity.

In this pilot study we will test the hypothesis that:

- 1) Guaifenesin use over a period of 14 days improves subjective nasal complaints in pediatric patients with chronic rhinitis and nasal congestion, as measured by the SN-5 survey compared to use of placebo.
- 2) There will be an observed improvement in nasal volume and cross-sectional area following use of guaifenesin, measured objectively using acoustic rhinometry compared to use of placebo.
- 3) Following treatment with guaifenesin, nasal secretions will have more favorable mucociliary and sneeze clearability compared to use of placebo.
- 4.) Children that respond and those that do not respond to guaifenesin therapy will show significant differences in mucus characteristics and mucociliary clearance.

Materials and Methods

Study Design

This is a 14-day, randomized, placebo-controlled, parallel group, masked clinical trial of oral guaifenesin for the therapy of CRS in 36 children between the ages of 7 and 18 years. A 2:1 ratio of subjects on active medication to placebo will be used. Before starting the study, this study will be approved by the Virginia Commonwealth University Institutional Review Board for human research. Study subjects will be assigned a unique coded identifier and all information will be entered into an Excel database in a password-protected computer, to which only the investigators have access. There is minimal risk to the child in acoustic rhinometry measurements, collecting nasal secretions, and completing the SN-5 surveys.

Subject Recruitment

We will enroll 36 subjects from the pediatric otolaryngology clinic at the Virginia Commonwealth University Medical Center in a 2:1 ratio of active medication to placebo. The subjects will be between the ages of 7 and 18 years at the time of the study. They will be identified during routine clinical evaluation for CRS as defined as chronic rhinitis and nasal stuffiness of at least 3 months duration. Informed consent will be obtained from the subject's parent or legal guardian and assent will be obtained from the study subjects. Given our clinic volume we anticipate that it will take 12 months to complete subject enrollment.

Children with immunodeficiency, cystic fibrosis, acute or subacute symptoms, signs of bacterial infection, and/or those who are unable to cooperate with testing will be excluded. Children with documented use of the study medication in the month before evaluation and during period of symptoms will also be excluded.

Parents of the subjects will complete the SN-5 questionnaire as described below, at initial evaluation and again during a lead-in phase three days later to ensure stability of symptoms. Patients with an improved score will be excluded.

The Sinus and Nasal Quality of Life Survey (SN-5)

The Sinus and Nasal Quality of Life Survey (SN-5) is a validated and reliable questionnaire designed to score five areas of impact from sinonasal dysfunction (SN-5) in patients 1 year to 18 years of age^{9,10}. Parents assess the impact of infection on nasal symptoms, emotion, and activity on a scale of worsening symptoms scored 1 through 7 to provide a quantifiable score capable of comparing both disease severity and the impact of interventions on subjective complaints. It has been shown as a responsive measure of health-related quality of life

for children with persistent sinonasal symptoms, suitable for use in outcomes studies and routine clinical care. Kay et al showed SN-5 test-retest reliability with an R value of 0.70⁹. Terrell et al demonstrated that the SN-5 correlated to disease severity as measured by the Lung-MacKay CT scan score¹¹.

Acoustic rhinometry

Acoustic rhinometry is used to measure cross-sectional volume of the nasal cavity allowing the calculation of nasal volume. Audible reflected sound waves are painlessly introduced through nasal adaptors into the nasal passages allowing the production of area-distance graphs. As the acoustic rhinometer is calibrated to a standard nose, accurate results can be obtained with good test-retest reliability^{12,13}.

Analysis of nasal secretions

Secretion collection

Collection and analysis of nasal secretions will be performed under direct vision at the time of rhinologic assessment. These will be collected using the Jun-Tymp-Tap (Xomed, Jacksonville, FL) as previously described¹⁴.

Mucociliary clearability

A mature leopard frog (*Rana pipiens*) is pithed and rapidly decapitated. The lower jaw is then disarticulated and the palate removed by cutting through from the junction of the posterior pharynx and esophagus out to the skin of the back. The excised palate is placed on a piece of gauze saturated with amphibian Ringer's solution and the palate is allowed to rest in a

refrigerator at 4°C for 12 hours to deplete of mucus. The palate is then placed in a Plexiglas box with a fitted top where humidity is maintained at 95-100% and temperature is kept at 24°C. The palate is focused under a microscope so that a 5 mm micrometer scale runs between the optic bulges to the opening of the esophagus. The movement of a 4 μ L mucus specimen is timed as the trailing edge moves across a 3 mm segment. Three measurements of mucus transport rate are taken to minimize variability¹⁵.

Dynamic viscoelasticity

Dynamic viscoelasticity measures the strain response of mucus to an applied stress. Because mucus is subjected to both low stress (ciliary beat) and high stress (sneeze) conditions, we measure the strain developed in response to a dynamic stress. Viscosity (loss modulus) is the loss of energy from a rheologic probe (stress) moving through a substance and thus the resistance to flow. Elasticity (storage modulus) is the recoil energy transmitted back to the probe. Viscoelasticity is a property of non-Newtonian fluids (gels). In the AR1500ex rheometer (TA Instruments, New Castle, DE), a parallel plate geometry is used to assess the dynamic frequency range of stress-strain of a 20 μ L nasal mucus sample over driving frequencies of 1 to 100 rad/sec. The viscosity G'' and the elasticity G' of the specimen are determined from these curves after non-destructive creep transformation. Rheologic data can also be presented using vectorial notation as tangent δ which is the ratio of viscosity to elasticity and G^* , the vector sum of viscosity and elasticity (mechanical impedance). The viscoelastic properties of a gel can be plotted using Cartesian coordinates (G' , G'') or vector notation (G^* , δ)¹⁶.

Study Protocol

After informed consent is obtained, a medical history will be obtained, including demographic data of personal or family history of allergies, asthma, nasal or sinus disease, exposure to tobacco smoke, prior medication history and other associated conditions. A head and neck physical examination will be performed, including a thorough rhinoscopic examination. We will determine nasal patency both by direct visualization and scoring and by acoustic rhinometry pretreatment and at post treatment follow-up, using the mean of three consecutive measurements. Secretions will be collected from the middle meatus pre and post treatment using the Jun-Tym-Tap. The SN-5 questionnaire will be completed at two baseline visits and after completion of the study.

The subject will be given a 14- day course of either guaifenesin or matched placebo to be taken orally three times daily according to following age-matched dosages: children aged 7-11 years old will receive guaifenesin 200 mg TID, while children older than 12 will receive guaifenesin 400 mg TID. Randomization of medication use will be carried out by a study participant not involved in the direct care of the patient. A 2:1 ratio of subjects on active medication to placebo will be used. After two weeks, the subject will return for data collection including nasal examination, SN-5, acoustic rhinometry, and collection of nasal secretions. Subjects that do not return for their follow up visit will be contacted to schedule repeat examination.

Data Analysis

Power calculation

The primary outcome variable will be changes in the SN-5 questionnaire score. It has been reported that the mean score in children with CRS is 3.8 with a standard deviation of 1.0 and a temporal effect size of standard therapy equal to 0.88¹¹. Thus assuming a normal distribution of results, using a paired 2-tail test to evaluate pre and post treatment outcome with an α error probability of 0.05 and a β (power) to detect a change of 0.88 at 80%, the critical t is 2.1788 yielding a sample size of 13 subjects per group¹⁷.

We will also compare pre and post treatment nasal patency scores based upon subjective direct visualization score of % obstruction by a single investigator and objective mean acoustic rhinometry values, and pre- and post treatment mucus biophysical properties. Collected data will be used to evaluate the outcome measures most predictive of therapeutic response. We will compare responders to non-responders to see if there are factors in the history, physical examination, demographics (e.g. tobacco smoke exposure), or baseline measurement that predict response to guaifenesin. These pilot data will be used to develop a focused controlled prospective study of children and adults most likely to respond to oral guaifenesin.

References

- 3.) Bailey BJ and JT Johnson. Head & Neck Surgery – Otolaryngology: Fourth Edition. Lippincott Williams & Wilkins. 2006:vol 1, 405-416.

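### 36 children at 2:1 puts 12 on placebo, one below the protocol's own 13 per group, and the power of the placebo comparison at 24 v 12 is not stated

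*Protocol*

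**What the plan says.** The Study Design section sets out a trial "in 36 children between the ages of 7 and 18 years. A 2:1 ratio of subjects on active medication to placebo will be used". The total is fixed again under Subject Recruitment: "We will enroll 36 subjects from the pediatric otolaryngology clinic". The ratio is repeated there and again under Study Protocol: "A 2:1 ratio of subjects on active medication to placebo will be used". Under Data Analysis, Power calculation, the primary endpoint is named: "The primary outcome variable will be changes in the SN-5 questionnaire score". The sample size is then obtained "using a paired 2-tail test to evaluate pre and post treatment outcome with an α error probability of 0.05", with 80% power for a change of 0.88, and the result is that "the critical t is 2.1788 yielding a sample size of 13 subjects per group".

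Hypotheses 1 to 3 are each worded as a comparison with placebo. Hypothesis 4 concerns children who do and do not respond to guaifenesin. The protocol does not connect 13 per group with the total of 36, gives no reason for the 2:1 ratio and states no allowance for loss. Children who miss the follow-up visit are to be contacted and rescheduled.

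**The concern.** The total and ratio in the design sections do not deliver the group size in the power section. A reader of the power section will take it that both groups have at least 13 children. One has 12.

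The reader also cannot tell from the protocol what 24 v 12 offers for the comparison with placebo, which is what hypotheses 1 to 3 are about. The smaller group dominates the standard error of that comparison, so it carries less information than the total of 36 suggests. At stake is an accurate account of what the pilot can show. The conduct of the trial is not affected.

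**Working it through.** **Inputs from the protocol.** Total 36; ratio 2:1; two-sided alpha 0.05; paired test; change to detect 0.88; SD of the SN-5 score 1.0; target power 80%; stated result 13 per group with critical t 2.1788.

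**Assumptions, not in the protocol.** The SD of the change in SN-5 is 1.0 in both arms (the protocol gives 1.0 only for the score itself). For the two-group calculation, 0.88 is read as a difference between arms, although the protocol reports it as a change over time under standard therapy. A range of 0.5 to 1.0 is therefore shown as well.

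**1. Reproduce the stated figure.** Paired t test, df = n − 1, noncentrality 0.88 × √n, power from the noncentral t distribution.

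- n = 13: df 12, critical t 2.1788, noncentrality 0.88 × √13 = 3.173, power 82.9%.
- n = 12: df 11, critical t 2.2010, noncentrality 0.88 × √12 = 3.048, power 79.2%.

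The stated critical t and sample size reproduce exactly. Thirteen is the smallest n that reaches 80%.

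**2. Apply the allocation.** Active 36 × 2/3 = 24; placebo 36 × 1/3 = 12. Since 12 < 13, the placebo group is one short at randomisation. Holding both 2:1 and 13 on placebo would take 26 + 13 = 39 children.

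**3. Information for the placebo comparison.** The variance of a difference in means is proportional to 1/n₁ + 1/n₂, assuming equal variance in the arms.

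- 24 v 12: 1/24 + 1/12 = 0.125.
- 16 v 16: 1/16 + 1/16 = 0.125, the same precision from 32 children.
- 18 v 18: 1/18 + 1/18 = 0.111.

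The ratio 0.125/0.111 is 1.125, so 2:1 carries 12.5% more variance than 1:1 with the same total. The standard error is √1.125 = 1.061 times as large; going to 1:1 would multiply it by 1/1.061 = 0.943, a reduction of about 6%. This step needs no effect size.

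**4. Power of the placebo comparison.** Two-sample t test, 34 df, critical t 2.032, noncentrality d/√(1/n₁ + 1/n₂).

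| Standardised difference d | 24 v 12 | 18 v 18 |
|---|---|---|
| 0.5 | 28.0% | 30.8% |
| 0.88 | 67.7% | 72.7% |
| 1.0 | 78.5% | 83.0% |

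At d = 0.88 and 24 v 12 the noncentrality is 0.88/√0.125 = 2.489.

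**5. What 1:1 would cost.** At any fixed responder proportion, the variance of a responder v non-responder contrast among treated children is inversely proportional to their number. Going from 24 to 18 multiplies it by 24/18 = 1.33, a rise of 33%, against the 12.5% excess removed for hypotheses 1 to 3.

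**6. Loss to follow-up.** Under 2:1, losing one placebo child raises the variance factor by (1/24 + 1/11)/0.125 − 1 = 6.1%, and losing one active child by (1/23 + 1/12)/0.125 − 1 = 1.4%. Averaged over a randomly lost child: (1/3) × 6.06% + (2/3) × 1.45% = 2.99%. Under 1:1 it is (1/18 + 1/17)/0.111 − 1 = 2.94%.

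**The case against.** The strongest reply is that the shortfall is one child and less than one point below the 80% target (79.2%), and that 13 is not the right yardstick for the placebo group anyway. It comes from a pre/post test within one group, and no hypothesis predicts that children on placebo will change by 0.88. In the active group, where a change is expected, the same calculation at n = 24 gives 98.5%. All of this stands. It limits the size of the point, but it does not reconcile the stated group size with the allocation.

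A reader might infer that 2:1 is itself a mistake and that the trial should be randomised 1:1. The protocol does not support that. Hypothesis 4, and the planned search for predictors of response under Data Analysis, draw on treated children, and the pilot is meant to inform a later study of likely responders. These aims are a plausible reason for 2:1, though the protocol does not give it. Working step 5 shows that 1:1 would trade one stated aim against another.

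A reader might also infer that 2:1 makes the trial more fragile to dropout. That is true for each placebo child lost, but only one child in three is on placebo. For a randomly lost child the cost is about 3% under either ratio, and nothing in the protocol suggests more dropout on placebo.

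**Conclusion.** The inconsistency is real and follows from the protocol's own numbers: 36 at 2:1 gives 12 on placebo, against a stated 13 per group. Its direct effect is small, 79.2% against 82.9% on the paired calculation. More useful to the reader is that the placebo comparison has the information of 16 v 16 and about 68% power at a standardised difference of 0.88, within a range of 28% to 78% for differences of 0.5 to 1.0. The 12 v 13 result needs no assumption, and the 16 v 16 equivalence needs only equal variances. The power figures rest on an SD of change of 1.0 and on reading 0.88 as a between-group difference.

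It does not follow that 1:1 is required, or that 1:1 would repair the power. 18 v 18 would meet 13 in both groups, but it reaches only 72.7% at 0.88, because 13 per group was never sized for a comparison between groups.

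**What to change.** In the Power calculation section:

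- Replace 13 per group with the sizes actually allocated, 24 active and 12 placebo.
- State that the placebo group is below the 13 from the paired calculation.
- State the power that 24 v 12 gives for the comparison with placebo: about 68% at a standardised difference of 0.88 with an SD of change of 1.0, and 28% to 78% for differences of 0.5 to 1.0.
- Add a sentence giving the reason for 2:1.

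This costs a few sentences and no extra children.

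The sponsor may separately weigh 1:1 with the same 36 children. The gain is a standard error about 6% smaller for hypotheses 1 to 3. The cost is six fewer treated children for the responder analyses, a lower chance of active drug for each family, and changes to the allocation text and the randomisation list. Either choice is defensible if the text states it.

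### The one-sided lead-in exclusion can bias a within-arm SN-5 pre/post test from either single baseline; the placebo comparison is not biased

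*Protocol*

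**What the plan says.** All references are to the protocol; no SAP is at hand.

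- **Subject Recruitment.** Parents complete the SN-5 at initial evaluation and "again during a lead-in phase three days later to ensure stability of symptoms". Then: "Patients with an improved score will be excluded". No size of improvement is given, and children who worsen are kept.
- **SN-5 section.** Higher scores are worse, on a 1 to 7 scale. A cited study is quoted for a test-retest R of 0.70.
- **Study Protocol.** "The SN-5 questionnaire will be completed at two baseline visits and after completion of the study". For acoustic rhinometry the protocol averages repeat readings, "using the mean of three consecutive measurements".
- **Power calculation.** The primary outcome is change in SN-5. The mean is given as 3.8 and the SD as 1.0. The sample size is found "using a paired 2-tail test to evaluate pre and post treatment outcome".
- **Hypothesis 1 and Study Design.** Guaifenesin is to be compared with placebo in 36 children randomized 2:1, that is 24 active and 12 placebo.

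**The concern.** The lead-in is meant to show that symptoms are stable, and screening out early improvers is a reasonable aim. But a questionnaire with R 0.70 moves between two sittings even when the child does not change. Dropping only the children whose score fell keeps those whose first score was low by chance or whose second was high by chance. Among them the two baselines err in opposite directions.

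A later score has no such selection, so in an unchanged child it drifts back to the true level. Measured from the lead-in score, that looks like improvement; measured from the first score, like worsening. A within-arm paired test can therefore report a change with no drug effect. At stake is any SN-5 conclusion drawn from such a test in a pilot meant to shape a later trial.

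**Working it through.** **The plan's own figure.** A two-sided paired t test with standardized change 0.88 and alpha 0.05 has power 0.829 at n = 13 (critical t 2.1788) and 0.792 at n = 12. The stated 13 reproduces.

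**Inputs.** SD 1.0 (power calculation); R 0.70 (SN-5 section); 24 and 12 children per arm (36 at 2:1). Assumed: no true change, no treatment effect, independent errors, and a child is kept if the second score is not below the first. The score step is not stated, so three are used: whole numbers, 0.2 points (the mean of five items) and continuous.

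**Closed form, continuous scores.**
- Error variance = 1.0² × (1 − 0.70) = 0.30, so error SD = 0.548.
- SD of the difference between two scores in an unchanged child = √(2 × 0.30) = 0.775.
- Mean error of the second score among children kept = (0.30 / 0.775) × 0.798 = 0.309. The first score has −0.309.
- Their mean has (0.309 − 0.309) / 2 = 0.
- Paired test from the lead-in score at n = 24: the variance of change among children kept is 0.505, so SE = √(0.505 / 24) = 0.145 and 0.309 / 0.145 = 2.13. This is close to the critical t on 23 df (2.07), so about half of such tests reject.

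**Simulation under the same assumptions.**

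| | Whole numbers | 0.2 steps | Continuous |
|---|---|---|---|
| Unchanged children excluded | 27% | 45% | 50% |
| Shift from the lead-in score | −0.21 | −0.28 | −0.31 |
| Shift from the first score | +0.21 | +0.28 | +0.31 |
| False significance from lead-in score, n = 24 | 24% | 45% | 53% |
| False significance from lead-in score, n = 12 | 12% | 23% | 28% |
| Mean of both: shift; false significance | 0.00; 5% | 0.00; 5% | 0.00; 5% |
| Variance of change, lead-in score to mean | 0.661 to 0.575 | 0.513 to 0.453 | 0.505 to 0.450 |

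The variance falls by 13%, 12% and 11%. Comparing arms (24 v 12), bias is 0.00 and type I error 5% with any baseline.

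**Parents who repeat their answers (assumed).** Let a share p give the same answers after three days and hold overall R at 0.70. The correlation in the others is then (0.70 − p) / (1 − p): 0.60 at p = 0.25 and 0.40 at p = 0.50. With 0.2 steps, exclusion falls to 34% and 23%, the shift to 0.20 and 0.14, and false significance at n = 24 to about 20% and 10%.

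**Real fluctuation over days (assumed).** If half of the non-stable variance is real, with a 3-day correlation of 0.6 to 0.8, the single-baseline shift is 0.20 to 0.27 and false significance at n = 24 is 28% to 42% (0.2 steps or continuous). Whole numbers give 0.15 to 0.17 and 15% to 17%. The mean gives 0.00 to 0.01 and 5%.

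**True change in the lead-in that lasts (assumed).**
- Average fall of 0.2 or 0.3: the mean shows 0.10 or 0.15 of improvement and 10–11% or 15–18% significance at n = 24. The lead-in score shows 0.27 to 0.41 and 36–79%. At 0.3 the first score does better than the mean (0.00 to 0.11; 5–11%).
- No average fall, but true changes with SD 0.3 or 0.5 between children (continuous): the shift is +0.37 or +0.48 from the first score, −0.29 or −0.26 from the lead-in score, and +0.04 or +0.11 from the mean. At SD 0.775, as large as the noise, the mean (+0.22) is no better than the lead-in score (−0.22).

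**The case against.** **The trial's question is unharmed.** Hypothesis 1 is against placebo, and selection on pre-treatment scores acts alike in both arms. This stands. The protocol does not say outright that randomization follows the lead-in, but it places the lead-in with recruitment and calls both scores baselines.

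**A within-arm test is weak anyway.** It cannot separate drug from natural course, and the paired test appears only as the basis for sample size. This partly stands: once the conclusion rests on placebo, the false-significance figures no longer bear on it, and averaging is mainly a modest gain in precision. But it is the only SN-5 test named, and Data Analysis goes on to further pre/post comparisons.

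**The baseline and the responder definition belong in a SAP.** This stands; their absence is not counted against the protocol. The exclusion is fixed in the protocol and cannot be undone in analysis.

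**The sizes rest on outside figures.** R and SD come from different cited studies, and the same parent answers twice within three days. This stands and widens the range. The continuous-scale figures are limiting values for a five-item score.

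**Stronger readings that a reader might infer.**
- *The enrollment forecast fails.* The protocol says "Given our clinic volume we anticipate that it will take 12 months to complete subject enrollment" but gives no clinic volume or accrual rate, so loss at screening cannot be tied to a delay.
- *The responder comparison is distorted by a known amount.* The plan states "We will compare responders to non-responders to see if there are factors in the history" but fixes no cut, so any figure would rest on an invented one.
- *The rule acts mainly on noise.* That depends on how much of R 0.70 is measurement error, which the protocol does not say.
- *Any improvement at all excludes.* That is the literal reading of an undefined word.

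**Conclusion.** The point holds for a within-arm SN-5 pre/post test taken from one baseline score. With SD 1.0, R 0.70, independent errors and no true change, the shift is about 0.2 to 0.3 points, and false significance at n = 24 is 24% to 53% instead of 5%. If 25% to 50% of parents repeat their answers, it is 0.14 to 0.20 points and 10% to 20%. The direction for each baseline is clear under these assumptions; the size is uncertain.

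The randomized comparison with placebo is not biased. The protocol supports no claim of missed enrollment and no sized claim about responders. Removing early improvers before a placebo comparison is a legitimate choice. This is a point to consider, with medium confidence.

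**What to change.** 1. State that the SN-5 conclusion rests on the comparison with placebo, as hypothesis 1 has it, and not on a within-arm paired test.
2. Use the mean of the two baseline SN-5 scores as the baseline value or covariate. This removes the shift if nothing truly changes in the lead-in. If something does, it usually reduces the shift; the exceptions are shown in the working. It lowers the variance of change by about 11% to 13% under independent errors.
3. Reconcile the wording on an improved score with the stated aim of stable symptoms and with the quoted reliability. Whether and at what size of change to exclude is the sponsor's decision; no cut-off is proposed.

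The cost is a few sentences, with no added visit or procedure. The downside of averaging is that the mean lags a true lead-in change by half, equally in both arms in expectation. That part is real change before treatment, not selection bias. If the sponsor sets a size of change under step 3, some children with a small real improvement would be kept.

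### The dosing rule does not clearly place eligible 12-year-olds in either of two age bands whose doses differ two-fold

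*Protocol*

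**What the plan says.** Under Subject Recruitment, the protocol sets eligibility by age: "The subjects will be between the ages of 7 and 18 years at the time of the study". The exclusions that close that section contain no age criterion: "Children with immunodeficiency, cystic fibrosis, acute or subacute symptoms, signs of bacterial infection, and/or those who are unable to cooperate with testing will be excluded". The two further exclusions concern recent use of the study drug and improvement of the SN-5 score during the lead-in. A 12-year-old can therefore be enrolled.

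The dose is fixed in one place, under Study Protocol: "children aged 7-11 years old will receive guaifenesin 200 mg TID, while children older than 12 will receive guaifenesin 400 mg TID". The clause that introduces it covers both arms: "14- day course of either guaifenesin or matched placebo to be taken orally three times daily according to following age-matched dosages". No other part of the protocol assigns a dose by age.

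Study Design gives 36 children and the allocation: "A 2:1 ratio of subjects on active medication to placebo will be used".

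**The concern.** The lower band ends with an inclusive whole number (11). The upper band begins with a strict inequality (above 12). Two bands written in these different ways need not meet, and the protocol states no age convention that would make them meet. The eligible range has no such gap.

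The sentence is operative: it decides which of two regimens a child on active drug takes, and which matched placebo a child in the other arm takes. Two members of staff could read it in good faith and supply different regimens to two children of the same age. The document does not show that this would happen, but it does not prevent it.

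There is also a minor analytic consequence. Data Analysis plans to look for demographic and baseline factors that predict response to guaifenesin. Dose is tied to age by design, so inconsistent dosing at one age would slightly blur that exploratory comparison.

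**Working it through.** **Inputs from the protocol**

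- Eligible ages: 7 to 18 (Subject Recruitment).
- Lower band: 7-11, 200 mg three times daily (Study Protocol).
- Upper band: above 12, 400 mg three times daily (Study Protocol).
- Duration: 14 days (Study Protocol).
- 36 children at 2:1 (Study Design): 36 × 2/3 = 24 on active drug and 36 × 1/3 = 12 on placebo.

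**Stated doses**

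- Per day: 3 × 200 = 600 mg against 3 × 400 = 1200 mg; ratio 1200/600 = 2.
- Over 14 days: 14 × 600 = 8,400 mg against 14 × 1200 = 16,800 mg.

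**Coverage of the eligible range**

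| Age convention | Lower band covers | Upper band covers | Left uncovered |
|---|---|---|---|
| Completed years for both bands | 7, 8, 9, 10, 11 (5 ages) | 13 to 18 (6 ages) | Age 12: 12 − 5 − 6 = 1 age |
| Exact age for both bands | 7th to 11th birthday | After the 12th birthday | The year from the 11th to the 12th birthday |
| Completed years for the lower band, exact age for the upper | Up to the day before the 12th birthday | From the day after the 12th birthday | The 12th birthday only |

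A single convention applied to both bands leaves a whole year of age without a stated dose. The gap shrinks to one day only if the reader changes convention within the sentence.

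**Expected number of children.** The protocol gives no age distribution, so these figures rest on assumption.

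- *Completed years, ages spread evenly over 12 whole-year ages:* share 1/12 = 8.3%. Overall 36/12 = 3; active 24/12 = 2; placebo 12/12 = 1.
- *18-year-olds not counted (11 ages):* active 24/11 = 2.2.
- *Half the even share (1/24):* active 24/24 = 1.
- *Double the even share (1/6):* active 24/6 = 4.
- *Past-the-birthday reading:* one day in 12 × 365.25 = 4,383 days; active 24/4,383 = 0.005, so about 0.

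In completed years, and treating children's ages as independent, the chance that at least one of the 24 active children is 12 is 1 − (11/12)^24 = 0.88 at the even share. It is 1 − (23/24)^24 = 0.64 at half and 1 − (5/6)^24 = 0.99 at double.

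**Sample size.** The Power calculation uses a standardised change of 0.88, a two-sided α of 0.05 and 80% power in a paired t test. With 13 pairs the critical t on 12 degrees of freedom is 2.1788, as stated, and the noncentral t gives power 0.829. With 12 pairs power is 0.792, so 13 is reproduced. Neither age nor dose enters the calculation, so the boundary cannot alter it. Whether a paired calculation suits a comparison with placebo is a separate matter.

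**The case against.** The strongest reply is that the sentence works on an ordinary reading. In everyday speech a child of twelve and a half is older than 12, and a child of eleven and a half is 11. The two bands are set against each other with no sign that any age was meant to be left out. On that view the wording is imprecise but not defective, and nobody would be at a loss over a dose. This reading is plausible and may be what was intended. It still asks the reader to switch age convention mid-sentence, and the protocol does not say so.

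A second reply is that inconsistent exposure is speculative. This is one clinic with 36 children, and one reading applied throughout would dose all 12-year-olds alike. That is fair: the protocol neither shows nor excludes inconsistency, so the point is a risk and not a demonstrated error in conduct.

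A third reply is that little turns on it scientifically. The active arm already pools both regimens by design, the two-fold difference is itself part of that design, and a child placed in either band receives a dose the protocol foresees. The comparison of guaifenesin with placebo stays intact. This stands, and it limits the weight of the finding.

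Finally, the estimated number of children runs from about 0 to 4 of 24 and depends on assumed ages. That also stands. The case for correcting the sentence rests on the gap in the rule and not on a particular count.

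**Conclusion.** The concern holds. The dosing sentence does not clearly place eligible 12-year-olds in either band, and the two bands carry stated daily totals of 600 mg and 1200 mg. The defect is an unclear boundary inside one sentence. It is not a direct contradiction between two statements in the protocol.

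On the active arm it touches about 0 children on the past-the-birthday reading and about 2 of 24 in completed years with evenly spread ages. The completed-years figure is 1 to 4 of 24 if the share aged 12 is half or double the even share. All these counts assume an age distribution that the protocol does not give; the gap and the two-fold ratio come directly from the text.

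The effect on the trial's conclusion is small. The correction is still worth making, because the sentence decides what a child is given.

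**What to change.** Reconcile the dosing sentence under Study Protocol with the age range under Subject Recruitment, so that every eligible age falls in exactly one band. State one age convention (for example, completed years at a named visit) and use it for both bands and for eligibility. Which band age 12 belongs to is for the investigator to decide; no dose is proposed here. The same wording should govern the matched placebo.

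The cost is a one-sentence correction to the protocol. Sample size, visits and analysis do not change.
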